Study topic: Lateral Ridge Augmentation Using Allograft Blocks and Guided Bone Regeneration for Implant Sites

Date:08/12/18

Study Summary

Background:

Clinicians are increasingly faced with the challenge of reconstructing the alveolar ridge as more patients desire fixed implant-supported restorations. Reconstruction of large horizontal alveolar defects still remains a challenge in implantology. Although autogenous blocks from intraoral sites are proven effective for such defects, donor site morbidity and limited graft availability are major limitations. Allogenic bone blocks have been proposed to overcome these limitations, however, the outcomes reported in the literature are inconclusive. Several case series (Acceturi 2002, Petrungaro 2005, Nissan 2008) claim successful ridge augmentation with allogenic bone, whereas others revealed higher failure rates due to bone exposure and graft resorption (Chiapasco 2013, Lumetti 2014, Spin-Neto 2013). In addition, allogenic bone blocks exhibit a higher degree of resorption (Spin-Neto 2013, Lumetti 2014), whereas Novell (2012), showed that resorption of allografts was comparable to autogenous bone blocks. Randomized clinical trials state that bone resorption occurs but does not deter successful placement of implants in augmented sites (Deluiz 2016, Amorfini 2014). This case series aims to evaluate the efficacy of allogenic blocks for lateral augmentation of atrophic ridges for implant sites, over a three-year period.

Materials and methods: In nineteen edentulous sites, cortico-cancellous allogenic blocks (PHOENIX, TBF, France) were shaped to the defect and screw-fixated. A double-layer of autogenous chips and demineralized bovine bone (Bio-Oss, Geistlich Pharma AG, Switzerland) was used to fill the voids. The augmented site was covered by non-cross-linked collagen membrane (Bio-Gide, Geistlich Pharma AG, Switzerland). After a healing period of 9 months, implants were placed and CBCT analysis was performed post-implantation. Following a period of 34 months of function, patients were clinically and radiographically re-examined. The primary outcome measure is the graft stability that is measured by change in lateral ridge width over time. Secondary outcome measures are various soft tissue parameters around the implant.

Study Protocol

Technique:

The present study design is a mono-center three-year follow-up case series study to examine the safety and effectiveness of allograft bone blocks combined with guided bone regeneration (GBR). The study is in accordance to the principles of the Declaration of Helsinki and will obtain approval by the standing ethical committee of the state of Bern, Switzerland.

The preoperative analysis includes a complete medical history, clinical examination of the dentition and a thorough analysis of the implant recipient using 3D cone beam computed tomography (3D Accuitomo 170, Morita, Kyoto, Japan).

Surgical Procedure:

The surgical procedures will be done in two stages. In the first stage surgery, a full-thickness mucoperiosteal flap will be raised on both the facial and palatal aspects. Ridge augmentation will be done using a mineralized, cortico-cancellous, delipidized, lyophilized allogenic block (ALB; PHOENIX allograft, TBF Mions, France). Following hydration of the ALB, the cortico-cancellous part of the block will be shaped to fit the recipient site and fixated by two fixation screws (Medartis, Modus, Mediartis Holding AG, Basel, Switzerland). Voids around the ALB will be filled with autogenous bone chips (AGB) harvested locally from the

recipient site. The augmented site will be covered by a first layer of deproteinized bovine bone mineral mixed (DBBM; Bio- Oss, Geistlich Pharma, Wolhusen, Switzerland and a non-crosslinked collagen membrane (BG; Bio- Gide, Geistlich AG, Wolhusen, Switzerland) as described previously (Chappuis 2017). A periosteal-releasing incision will be used to provide tension-free flap closure. The wound margins will be approximated using non-resorbable poly- amide suture (Seralon, Serag-Wiessner GmbH, Naila, Germany) to obtain primary wound closure. All patients will be prescribed an antibiotic regimen with 2g of amoxicillin with clavulanic acid 1 hour preoperatively to be continued as 1g twice daily for 3 days post-surgery. Patients will be also prescribed analgesics and chlorhexidine digluconate (0.2%) for chemical plaque control. In patients with post-surgical complications the antibiotic regimen will be prolonged. Sutures will be removed around 14 days postoperatively. Removable provisionals will be adapted, but patients will be instructed to not to wear them unless unavoidable during the initial healing phase.

The second stage surgery will be performed after a minimal healing period of six months. A paracrestal incision will be given to elevate a full thickness mucoperiosteal. The fixation screws from the previous surgery will be removed and the implant bed will be prepared based on the specific requirements of the site. All implants placed will have chemically modified, sandblasted, and acid-etched surface and will have either, a tissue level implant (TL) or a bone level implant (BL) design (SLActive, Straumann AG, Basel, Switzerland).

Simultaneous re-grafting will be performed as required using autogenous bone chips, DBBM and a non-cross-linked collagen membrane. A tension-free wound closure will be obtained by non-resorbable sutures. The antibiotic and analgesic regimen and post-surgical care will be the same as in the first-stage surgery. Sutures will be removed after 14 days. Patients will be instructed to wear the provisional with caution. After a healing period of 4-6 months the healing abutments will be placed for the future prosthetics. The implants will be restored with either different prosthetic solutions as required. Patient will be given oral hygiene instructions and directed to enroll onto a supportive periodontal therapy to monitor oral health.

Clinical and radiographic follow-up examination after 3 years:

Clinical parameters - Updates on medical conditions, smoking, oral hygiene and enrollment in a maintenance care program will be collected from the patients. Clinical examinations will be made by the same examiner throughout the three-year follow-up period. The clinical parameters will be assessed as previously described (Chappuis 2017): peri-implant suppuration, modified plaque index (mPLI), modified sulcus bleeding index (mBLI), probing depth, DIM (distance from the implant shoulder to the mucosal margin), width of the KM, mobility and full mouth plaque scores.

Radiographic analysis using 2D radiographs and 3D CBCT - The peri-implant bone loss will be measured on periapical 2D radiographs analyzing the proximal DIB values as the vertical distance from the implant shoulder to the first bone-to-implant contact as described earlier (DIB; mm) (Weber HP et al 1992). The mean DIB value per implant considered will be the average of the mesial and distal values.

The horizontal bone gain of the atrophic sites will be assessed by with the smallest field of view (3D Accuitomo 170, Morita, Kyoto, Japan). The image analysis will be performed by a high-resolution screen, using a specialized software (i-Dixel, Morita, Kyoto, Japan). The 3D analysis included a preoperative analysis of the proposed implant site. A standard reference point, 4mm crestal to the shoulder of the future implant will be used for all measurements (Chappuis 2017). CBCT measurements will be repeated prior to implant placement, using

the same reference point and repeated again at the 2-3 year follow-up appointment. The radiographic measurements will be done by one examiner.

Assessment of biological, technical complications and patient reported outcome measures (PROMS) - All events of complications, intra-operative and post-operative at each surgical phase (graft surgery and implant surgery), prior to prosthetic treatment and post prosthetic rehabilitation both operator-assessed and self-reported will be recorded.

Patient reported outcome measures will be assessed by the Oral Health Impact Profile (OHIP) scores and patient satisfaction scores based on a visual analog scale (VAS) will be recorded for each patient after the entire treatment is completed and the patients receive the prosthetic replacements.

References

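### Re-grafting at implant placement can add to the ridge width by which graft stability is judged, and it is not a named outcome

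*Protocol*

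**What the plan says.** The Study Summary (Materials and methods) defines the endpoint: "The primary outcome measure is the graft stability that is measured by change in lateral ridge width over time". It adds: "Secondary outcome measures are various soft tissue parameters around the implant". The series is sized by sites: "In nineteen edentulous sites, cortico-cancellous allogenic blocks (PHOENIX, TBF, France) were shaped to the defect and screw-fixated".

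Under Surgical Procedure, the second-stage surgery includes this provision: "Simultaneous re-grafting will be performed as required using autogenous bone chips, DBBM and a non-cross-linked collagen membrane". Neither a criterion nor a reason is given.

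The timing of the middle scan is stated in two ways. The radiographic section of the follow-up examination says "CBCT measurements will be repeated prior to implant placement, using" and continues "the same reference point and repeated again at the 2-3 year follow-up appointment". The Study Summary says "After a healing period of 9 months, implants were placed and CBCT analysis was performed post-implantation".

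On events, the section on complications and patient-reported outcomes records "All events of complications, intra-operative and post-operative at each surgical phase". It does not mention re-grafting.

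**The concern.** The endpoint is named for the graft, but it is measured on a ridge to which the protocol allows more bone material to be added partway through. A width reading does not show which operation produced the bone. At a re-grafted site, the follow-up width is whatever remains of the original graft plus whatever remains of the second one.

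The Background presents resorption of allogenic blocks as the open question. If an original graft loses width and a second graft replaces it, the site can read as stable. The fact that more material was needed is itself informative about the original graft, yet it is not a named outcome. A reader of the results could then not tell a ridge that held from one that was rebuilt.

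**Working it through.** The protocol states no effect size, variability, re-graft frequency or width gain from re-grafting, so there is no figure of its own to reproduce. The check consists of the order of events and a simple formula.

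**Order of events at a re-grafted site**

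| Interval | Middle scan before implant placement (radiographic section) | Middle scan after implant placement (Study Summary) |
|---|---|---|
| Preoperative to middle scan | No second graft in either scan | Second graft adds to the later width |
| Middle scan to follow-up | Second graft adds to the later width | Second graft in both scans; change is that of both grafts together |
| Preoperative to follow-up | Second graft adds to the later width | Second graft adds to the later width |

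Under the radiographic section's timing, one interval is free of the second graft. Under the Study Summary's timing, none is. The total change is affected either way.

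**Size of the shift**

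Inputs:
- n = 19 sites, from the Study Summary, taking all of them to have a follow-up scan.
- k = number of sites re-grafted. Not in the protocol; assumed 2 to 8.
- g = width from the second graft still present at the measured level, in mm. Not in the protocol; assumed 0 to 2. Zero belongs in the range because nothing says re-grafting adds width at that level.

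Wherever the table says the second graft adds to the later width, the mean change moves upward by k × g / n. (Where that later width is the middle scan, g is the amount present at that scan.) One site retaining 1 mm contributes 1/19 = 0.053 mm.

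| k | g = 0 | g = 1.0 | g = 1.5 | g = 2.0 |
|---|---|---|---|---|
| 2 | 0 | 0.11 | 0.16 | 0.21 |
| 4 | 0 | 0.21 | 0.32 | 0.42 |
| 6 | 0 | 0.32 | 0.47 | 0.63 |
| 8 | 0 | 0.42 | 0.63 | 0.84 |

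For example, 4 × 1.5 / 19 = 0.32 mm.

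**What this could do to a mean (illustration only)**

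Assume a change from the pre-implant scan to follow-up of −0.3 mm at sites not re-grafted and, for the original graft alone, −1.5 mm at re-grafted sites. With k = 4:
- Original graft alone: (15 × −0.3 + 4 × −1.5) / 19 = −10.5 / 19 = −0.55 mm.
- Observed with g = 1.5: (15 × −0.3 + 4 × 0) / 19 = −4.5 / 19 = −0.24 mm.
- Observed with g = 0: −0.55 mm, so no shift.

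In the second line the re-grafted sites read as exactly stable because the assumed loss and gain were set equal. It shows what can happen, not what will.

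**The case against.** **The treatment is block plus GBR.** The title and the Technique section describe allograft blocks combined with guided bone regeneration, and the first-stage graft already uses bone chips, DBBM and a collagen membrane. On that view the width is never that of the block alone, and re-grafting belongs to a two-stage treatment whose total result is a legitimate target. This stands for an all-site result labelled as such. It does not cover a statement that the original graft was stable, because a second graft months later is a further addition.

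**A clean interval is planned.** With a scan before implant placement, poor early gain would be visible. This stands under the radiographic section's timing, so it cannot be said that the resorption question goes unanswered at re-grafted sites. The later and total changes remain affected, and the Study Summary's timing removes the clean interval.

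**The analysis may be in an SAP.** The protocol does not say that all sites enter one pooled width change, and a reader should not infer it. How subgroups are tabulated may be settled in an analysis plan not seen here. What the protocol does fix is the outcome definition and the list of outcomes, and re-grafting is absent from that list.

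**The reason for re-grafting is unknown.** It is tempting to infer that re-grafting goes to the sites where the block did worst, and hence that the result must be biased in the block's favour. The protocol gives no reason; contour or bone around the implant would fit the wording equally well. Nor does it say whether re-grafting would be logged as a complication. Only the conditional statement is supported: width retained from a second graft, if any, moves the change upward.

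**Conclusion.** The point holds in conditional form. As the protocol is written, any width retained from a second graft is credited to graft stability in the total change. It is also credited in the change from the pre-implant scan to follow-up if the middle scan precedes implant placement. The early change is clean under that timing and is affected under the Study Summary's timing; the two statements must be reconciled.

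The shift is k × g / 19 mm, upward or zero. Under the assumed ranges it is 0 to 0.84 mm. Its true size is unknown, because the protocol gives neither how often re-grafting occurs nor what width it adds. The conclusion itself needs only the order of the procedures and scans, and the absence of re-grafting from the named outcomes.

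**What to change.** - Record re-grafting per site at the second surgery: yes or no, and the reason.
- Name the proportion of grafted sites that were re-grafted as a reported outcome.
- Report the primary width change descriptively for sites with and without re-grafting.
- Label the all-site width change as the result of the overall two-stage treatment.
- Limit statements about stability of the original block and GBR graft after implant placement to sites not re-grafted.
- Reconcile the two statements on the middle scan, so that it is clear which intervals contain the second graft.

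The cost is a short entry per site and one extra table. With nineteen sites the subgroups will be small and should stay descriptive: a re-graft count of 4 of 19 would be 21.1%, with an exact 95% interval of 6.1 to 45.6%. The headline may also be less favourable. No change to when re-grafting is done is proposed.

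### The study is labelled three-year, but the final CBCT for the primary ridge-width outcome is scheduled at 2-3 years, with no time origin and no settled post-graft reference scan

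*Protocol*

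**What the plan says.** On the length of follow-up:

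- Study Summary, Background (aim): the blocks are evaluated "for lateral augmentation of atrophic ridges for implant sites, over a three-year period".
- Study Protocol, opening design statement: "The present study design is a mono-center three-year follow-up case series study".
- Study Protocol, heading of the follow-up section: "Clinical and radiographic follow-up examination after 3 years". This heading expressly covers the radiographic work.
- Study Protocol, radiographic analysis, under that same heading: the CBCT is taken with "the same reference point and repeated again at the 2-3 year follow-up appointment".
- Study Summary, Materials and methods: "Following a period of 34 months of function, patients were clinically and radiographically re-examined". This is the only follow-up figure tied to an event (time in function).

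On the outcome, the Summary states: "The primary outcome measure is the graft stability that is measured by change in lateral ridge width over time". No time point is attached to it.

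On the scan between grafting and final follow-up, the radiographic analysis section says "CBCT measurements will be repeated prior to implant placement", while the Summary says "implants were placed and CBCT analysis was performed post-implantation". The description of the second-stage surgery allows additional grafting at implant placement where it is needed.

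**The concern.** The study asks whether the grafted width holds over time, and the protocol's own Background says the literature disagrees on how much allograft blocks resorb. The interval between scans is therefore part of the result. If final scans may fall anywhere from 24 to 36 months, width changes over different intervals are pooled under one three-year label. Should width still be changing between years 2 and 3, the earlier scans misstate the three-year value; should it have plateaued, they do not.

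The other end of the interval matters as much. A scan before implant placement excludes any bone added at placement, while the final scan includes whatever remains of it. The difference between the two then mixes loss of the block with gain from the second graft.

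What is at stake is the descriptive three-year statement of a case series of nineteen sites. No between-group comparison and no error rate is involved.

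**Working it through.** **Inputs**

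- Horizon: 3 years (aim, design statement, follow-up heading) = 3 × 12 = 36 months.
- Final CBCT: 2-3 years (radiographic analysis) = 24 to 36 months.
- Grafting to implant placement: at least 6 months (second-stage surgery); 9 months (Summary).
- Implant placement to healing abutment: 4-6 months (second-stage surgery).
- Re-examination: 34 months of function (Summary).

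The protocol gives no calculation of its own to reproduce, so the check is interval arithmetic.

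**Step 1: one common origin.** Shortfall = 36 − scan time.

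- Scan at 36 months: 36 − 36 = 0.
- Scan at 24 months: 36 − 24 = 12 months; 12/36 = 33.3%.

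**Step 2: three years counted from grafting, 2-3 years from a later event.** The earliest scan is at 24 months on the later clock.

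| 2-3 year count starts at | Months since grafting | Short of 36 |
|---|---|---|
| Implant placement, 6 months after grafting | 24 + 6 = 30 | 6 |
| Implant placement, 9 months after grafting | 24 + 9 = 33 | 3 |
| Abutment, 6 + 4 months after grafting | 24 + 10 = 34 | 2 |
| Abutment, 6 + 6 months after grafting | 24 + 12 = 36 | 0 |
| Abutment, 9 + 4 months after grafting | 24 + 13 = 37 | none |
| Abutment, 9 + 6 months after grafting | 24 + 15 = 39 | none |

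If three years ran from implant placement and 2-3 years from abutment placement, the earliest scan is at 24 + 4 = 28 to 24 + 6 = 30 months, which is 8 to 6 months short. In every case where the 2-3 year count starts later, the gap is below 12 months or absent. The reverse order would widen it. The document supports neither order; because the CBCT sentence sits under the three-year heading, one visit and one origin is the natural reading.

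**Step 3: where the 34 months fall.** Assume function starts no earlier than abutment placement.

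- Since implant placement: at least 34 + 4 = 38 months.
- Since grafting: at least 34 + 4 + 6 = 44 months. With the Summary's 9-month healing, 34 + 4 + 9 = 47 to 34 + 6 + 9 = 49 months.

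Counted from either surgery, the re-examination is past three years.

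**Step 4: the reference scan.** Let W be the width before implant placement, G the width added by re-grafting, and R the total loss up to the final scan. Final width = W + G − R.

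- Change from a scan before placement: (W + G − R) − W = G − R.
- Change from a scan just after placement: (W + G − R) − (W + G) = −R.

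The first reads as stable whenever G is close to R, however large R is. The second shows the loss, but of block and added graft together. At a site without re-grafting G = 0, so this effect disappears. The protocol gives no frequency or size for re-grafting, so G cannot be filled in.

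**The case against.** The strongest reply is that 2-3 years is only a loose label for the three-year visit. The CBCT sentence sits under the three-year heading, the ranges meet at 36 months, and the one anchored figure, 34 months, lies inside the window and rounds to three years. This benign reading fits every statement, so the text is not a flat contradiction. A reader might infer that a 24-month scan complies with the protocol. On a common origin it satisfies the scheduling sentence but not the heading above it, and nothing shows that such a scan was taken. What remains is that the sentence fixing the last primary measurement allows a year that the label does not.

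A reader might also subtract 34 from 36 and call the re-examination two months short. That sets time in function against a horizon with no stated origin, and Step 3 shows that the sign can reverse. The figure should not be used.

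Nor is a three-year primary endpoint contradicted: the outcome sentence says only that change is measured over time. The three-year label comes from the aim, the design statement and the heading.

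On the intermediate scan, a reader might infer that the Summary and the body contradict each other. The post-implantation CBCT could be an additional scan, and the Summary does not say that it replaces the earlier one. Even so, the protocol does not say which scan is the reference for stability.

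Finally, per-site intervals could be specified in an analysis plan that is not shown. That is fair for the reporting detail. The scan schedule and the three-year label, however, are set in the protocol itself and need to agree there.

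**Conclusion.** The point holds as an inconsistency in how the primary measurement interval is fixed, and it should be corrected. At the far end, the scheduling sentence allows a scan up to 12 months (one third) short of the stated three years. That maximum assumes both figures run from the same unnamed event; it is a limit of the wording, not an observed gap. At the near end, the reference scan for graft stability is not settled. If it is the scan before implant placement, bone added at re-grafting can be counted as stability of the block.

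The documents do not support any statement about bias in millimetres: no resorption rate between years 2 and 3, no re-grafting frequency and no scan dates are given. The consequence is limited to what a descriptive case series can claim about three-year stability.

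**What to change.** 1. Reconcile the aim, the design statement, the follow-up heading and the CBCT sentence to one final time point counted from one named event; the Summary already uses time in function. If 2-3 years is what is meant, or if the scans are already taken, as the Summary's past tense suggests, call the study a 2-3 year follow-up throughout.
2. State which post-graft scan is the reference for graft stability, and whether the post-implantation CBCT in the Summary is that scan or an additional one.
3. Report each site's actual interval from that reference scan to the final CBCT beside its width change.
4. Identify re-grafted sites. If the pre-placement scan is the reference, show stability with and without them.
5. Keep the preoperative scan as the baseline for bone gain, since it precedes grafting.

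The cost is protocol wording, two scan dates per site and one re-grafting indicator, with no extra imaging. The downside is that the three-year claim may become 2-3 years and that some of the nineteen sites may have to be reported separately.

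### The primary CBCT ridge width appears to be read visit by visit by one examiner with earlier values not hidden, so drift or anchoring can bias the mean change; a deferred, coded, random-order reading would reduce this risk cheaply

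*Protocol*

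**What the plan says.** The Study Summary defines the endpoint: "The primary outcome measure is the graft stability that is measured by change in lateral ridge width over time". It gives the size of the series as nineteen sites. The Technique section calls the study a "mono-center three-year follow-up case series study", and no comparison group is described.

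The section on radiographic analysis using 2D radiographs and 3D CBCT sets out three width measurements:

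- **Preoperative:** "The 3D analysis included a preoperative analysis of the proposed implant site".
- **Before implants:** "CBCT measurements will be repeated prior to implant placement".
- **Follow-up:** the preceding sentence continues with "the same reference point and repeated again at the 2-3 year follow-up appointment".

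The level of measurement is a standard landmark, 4 mm from the shoulder of the planned implant, and is common to all measurements. On who reads the scans, the section says: "The radiographic measurements will be done by one examiner". It does not say when the stored images are read, in what order, or whether the examiner can see earlier widths.

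**The concern.** The endpoint is a within-site difference between manual readings. If the readings are made as each visit occurs, the first and last are years apart. Two systematic errors then become possible.

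- **Drift.** The examiner's way of placing the bone margins may change between visits. If it changes in the same direction for most sites, the mean change moves by that amount.
- **Anchoring.** An examiner who knows the earlier width may place the new one closer to it, which pulls the measured change toward zero. From the pre-implant scan to follow-up this understates resorption, the favourable direction for an outcome called graft stability. From the preoperative to the pre-implant scan it understates the bone gain, which is unfavourable. The direction therefore depends on which change is reported.

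Neither error averages out with more sites, no control group cancels it, and the confidence interval does not reflect it. The Study Summary describes the literature on allograft resorption as conflicting, so a procedure that could understate resorption bears on the question the study asks.

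**Working it through.** The Protocol gives no SD of change, expected change, test, power or reader-error figure, so there is no stated figure to reproduce. The calculations below show scale only.

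**Inputs**

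- Number of sites: n = 19 (Study Summary, Materials and methods), treated as independent. The number of patients is not given.
- SD of site-level change: 0.5, 1.0 or 1.5 mm (assumed).
- Drift b between visits, common to all sites: 0.1 to 0.5 mm (assumed).
- Anchoring weight w: 0.1 to 0.3 (assumed).

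**Step 1: precision.** SE = SD/√19, and the 95% half-width is t(0.975; 18 df) × SE, with t = 2.101.

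| SD (mm) | SE (mm) | Half-width (mm) |
|---|---|---|
| 0.5 | 0.115 | 0.24 |
| 1.0 | 0.229 | 0.48 |
| 1.5 | 0.344 | 0.72 |

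**Step 2: drift.** Observed mean change = true mean change + b. The bias is b whatever n is. The t statistic for zero change, when the true change is zero, is noncentral t with 18 df and noncentrality b/SE. For b = 0.25 mm:

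| SD (mm) | Noncentrality | Rejection at nominal 5% |
|---|---|---|
| 0.5 | 2.18 | 54.1% |
| 1.0 | 1.09 | 17.8% |
| 1.5 | 0.73 | 10.6% |

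The same distribution gives the actual coverage of a nominal 95% interval for the mean change, whatever the true change is:

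| Drift b (mm) | SD 0.5 | SD 1.0 | SD 1.5 |
|---|---|---|---|
| 0.1 | 87% | 93% | 94% |
| 0.2 | 62% | 87% | 92% |
| 0.5 | 2% | 46% | 72% |

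**Step 3: anchoring.** Observed change = (1 − w) × true change. With w from 0.1 to 0.3, an assumed true loss of 1.0 mm is read as 0.9 to 0.7 mm, and an assumed gain of 4.0 mm as 3.6 to 2.8 mm. With no true change, anchoring adds nothing, so the rejection rates in Step 2 concern drift alone.

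**Step 4: effect of the reading order.** When scans are read in one period, in random order across sites and time points, any drift within that period falls on all time points alike in expectation. It becomes noise rather than a shift between visits. Hiding recorded widths removes anchoring on those values.

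**The case against.** The strongest objection is that the text does not establish the mechanism. A reader of the Protocol might infer that the examiner must open the earlier measurement to find the reference point, and so sees the earlier width. The document does not support that. The point is a landmark tied to the implant shoulder, which is present on the follow-up scan, and any change measure needs a common landmark. What remains is weaker: before placement the shoulder exists only as a plan, so returning to the same level plausibly means consulting the planning, and nothing hides the earlier width.

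It can also be said that visit-by-visit reading is itself an inference. The repeats may describe when scans are taken, and the Study Summary reports treatment and 34 months of function in the past tense, so a later batch reading is possible. This stands in part. The text says that measurements are repeated and ties the last to an appointment, so sequential reading is the natural sense, but it is not the only one.

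A reader might further infer that the mean change will be biased, or that the operating surgeon does the reading. The Protocol gives no reader-error data and does not identify the examiner, so neither can be asserted. The illustrative figures depend on an assumed drift and SD and on a zero-change test that the Protocol does not name.

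On the remedy, reading the three scans of a site back to back could itself cause anchoring on a width measured minutes before. That objection is correct and shapes the fix.

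Finally, reading order might be set in a document not shown. However, how the primary outcome is measured is a procedure that this section of the Protocol itself sets out, and it does so without protection against these errors.

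**Conclusion.** The point holds as a risk to the primary outcome, not as a demonstrated bias. On its natural reading, the Protocol has one examiner measure ridge width at successive visits, without masking of earlier values, in a study with no control group. Drift between visits would pass into the mean change in full, and knowledge of earlier values would shrink the measured change. The document does not allow the amount to be estimated. Under the stated assumptions the consequence of a 0.2 mm drift ranges from slight (coverage 92% at SD 1.5 mm) to serious (62% at SD 0.5 mm).

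This is not a fatal flaw. It is an inexpensive safeguard that the sponsor should adopt. If a deferred batch reading is already intended, the text should say so.

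**What to change.** Add to the section on radiographic analysis using 2D radiographs and 3D CBCT:

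- Widths for the primary outcome are read by the same single examiner, in one reading period, after the last scan is available.
- Scans are coded and read in random order across sites and time points, not with the three scans of a site back to back.
- Earlier width values and the clinical outcome are hidden. The reference level may be transferred from the planning without showing the earlier width.
- Visit-time readings serve treatment planning only and are not used for the primary outcome.
- Preferably the examiner did not operate on the sites. This should remain a preference, because making it a requirement could call for an extra reader.

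A repeat reading of a subset would be a useful optional addition, since it would show the size of intra-examiner error.

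**Cost.** The core change is a sentence or two of text, with no extra scan, visit or reader. Stored scans have to be re-read, and the outcome readings wait for the last scan. Masking is partial because fixation screws and implants reveal the time point, so some expectation bias remains.
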